#### 4. Study Endpoints

##### 4.1 Primary Safety Endpoints

Incidence of clinically significant pre-discharge (both intra- and post-operative) blood transfusion, clinically significant hematoma development, or return to the operating room for bleeding; post-operative renal failure; and post-operative morbidity rates.

##### 4.2 Secondary Endpoints

A number of exploratory biological correlative studies including transcriptome analysis, flow cytometry, TCR sequencing and single cell RNA Seq to evaluate the effects of ketorolac on immune response pathways.

## 5. Study Intervention/Investigational Agent

### 5.1 Surgical Resection

All patients will receive standard-of-care surgery. Open, video-assisted thoracic surgery, laparoscopy, or robotic surgery are allowed. Standard anesthesia will be administered.

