## 1. Study Summary

Study Title	A Pilot Study of Biomarker Evaluation and Safety of Pre-Incisional Ketorolac for Patients Undergoing Surgical Resection for Non-Small Cell Lung Cancer and Renal Cell Carcinoma
Study Design	
PATIENT REGISTRATION/RANDOMIZATION
 
Patients will be screened and recruited during the pre-operative period by the responsible medical and surgical team. Blood will be drawn pre-operatively and then at the end of the surgical procedure. Patients who are eligible to be included will be fully informed, consented for additional blood draws and will have the opportunity to ask any questions they may have.
 
Patients will be randomized to either pre-operative Ketorolac group or a concurrent control group who will not receive pre-incisional ketorolac. The concurrent control group is to obtain untreated biologic samples for biologic correlative studies and secondary endpoints. These patients will not be compared to the investigational cohort in regards to the primary endpoint of safety. Patients will be randomized on the day of surgery to either the experimental or control arms. A total of 56 patients will be enrolled into the experimental arm (28 per disease site). About 10 patients will be allocated randomly into the concurrent control group for each disease site separately, for a total of 76 patients enrolled. The enrolment for NSCLC will cease at total of 28 patients consented with total study enrolment goal of 79 Up to 80 patients may be consented on study to account for screen fails and/or withdrawals.

Primary Objective	To test the safety of a single pre-incisional dose of 30 mg ketorolac in patients undergoing surgery for stage I/II NSCLC and stage III RCC, as these are the stages of cancer most likely to develop a recurrence while still noting a benefit from the ketorolac.
Secondary Objective(s)	To evaluate blood and tissue samples pre- and post-operatively to assess the impact of ketorolac on key

	inflammatory biomarkers using a standard cytokine panel.

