## 3. Introduction and Background

[figure not shown]
Surgical resection is a cornerstone of standard-of-care treatment for early-stage non-small cell lung carcinoma (NSCLC) and renal cell carcinoma (RCC). Yet despite optimal treatment, many of these patients will develop cancer recurrence within the first few years. For example, the 5-year

survival rate for patients with stage I/II NSCLC is only around 55%. As a result, more effective treatments that decrease cancer recurrence and increase survival are still needed.

Surgery induces inflammation, immunosuppression and angiogenesis. Although these processes are important for wound healing in response to tissue injury caused by surgery, they also support the survival, growth and dissemination of any remaining cancer cells and can lead to systemic recurrence soon after surgery. Surgical trauma increases the production of prostaglandins and thromboxanes, which have tumor-promoting and immunosuppressive activities, and reduces the activity of natural killer cells, which impairs the ability of the immune system to keep cancer cells in check. However, if given just before tissue injury, non-steroidal anti-inflammatory drugs (NSAIDs) may be able to block the production of prostaglandins/thromboxanes and boost the activity of natural killer cells, and thereby decrease the risk of cancer recurrence. Indeed, NSAIDs have anticancer effects in animal models and humans. For example, in one study, the 20-year risk of cancer-related death was significantly lower after administration of daily aspirin (HR 0.80,  $p<0.0001$ ).

NSAIDs such as ketorolac are already routinely given to cancer patients post-operatively for pain management and are sometimes given intra-operatively (immediately before or during surgery) to prevent post-operative pain. A retrospective clinical analysis found that intra-operative intravenous ketorolac or diclofenac (another NSAID), when added to standard of care for patients with stage I/II NSCLC, was associated with decreased risks of distant recurrence (HR = 0.50; 95% CI 0.24-1.00;  $P = 0.05$ ) and mortality (HR = 0.64; 95% CI 0.42-0.96;  $P = 0.03$ ) (Figure 1). Similar results were seen in renal cell carcinoma (RCC).

**Figure 1.** Kaplan-Meier curves of overall survival for 255 patients receiving or not an NSAID (ketorolac or diclofenac) intra-operatively during NSCLC surgery. Univariate analysis by log-rank test. Figure from .

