## 7. Data and Specimen Banking

### 7.1 Biological Correlative Studies

The specific effects of ketorolac on the host immune system are not known. It is hypothesized that pre-operative ketorolac will enhance anti-tumor immunity and result in activation of tumor-specific T cell responses, as has been noted in our preclinical studies. To verify this, we will collect tissue samples, including surrounding benign and malignant tissue as part of the standard surgical procedure, and peripheral blood at pre-specified time-points. The following samples will be collected from all patients on this trial:

1. Tumor tissue at the time of surgery - Tissue will be collected from patients at the time of surgery by clinical research coordinators from the Clinical Research Unit and taken to [name] lab if adequate tissue is available after all necessary clinical samples are obtained as determined by the pathologist. Tissue analysis will be performed on malignant and benign tissue.
2. Serum and PBMCs before and at time points after surgery - Blood will be collected in CPT from patients at the time of surgery and postoperatively, as delineated in the timeline, by clinical research coordinators.

The following studies are planned in the bio-specimens collected: 1. Flow cytometry (at least to assess proliferating and activated T-cells in blood); 2. TCR sequencing to assess diversity of the T cell repertoire intra tumorally and in blood; and 3. Single cell RNA Seq in blood. Samples will be suitably prepared to allow for this at a future date. Collectively these assays will provide evidence for whether pre-op ketorolac can unleash post-operative anti-tumor T cell response in humans, thus extending the mouse data above. In addition, we will measure NLR, CRP, and IL-6 – all of which have been correlated to prognosis in a number of tumor types at baseline and some of which have been correlated to recurrence outcomes. Additional exploratory studies may also be conducted based on the results of these studies. Peripheral blood mononuclear cells (PBMCs) and plasma will be isolated from CPTs and cryopreserved. The correlative work will be conducted in the lab of [name], [name] and [name].

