#### 16.2.4 Analysis of the secondary endpoints

For all biomarkers, descriptive statistics (means, medians, standard deviations, interquartile range) and graphical displays will be used to characterize central tendency and variability over time. Values will be log transformed as appropriate to reflect biologic plausibility.

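### The biomarker analysis has no arm contrast and ignores surgical approach, although approach is unrestricted and the controls exist for the biomarker question

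*Combined protocol and SAP*

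**What the plan says.** - **Surgery and anaesthesia.** Section 5.1, repeated in Section 6.2.1 and the Study Summary, sets no restriction on approach and does not define the anaesthesia further: "Open, video-assisted thoracic surgery, laparoscopy, or robotic surgery are allowed. Standard anesthesia will be administered".
- **Biology.** Section 3 states: "Surgery induces inflammation, immunosuppression and angiogenesis". It continues: "Surgical trauma increases the production of prostaglandins and thromboxanes, which have tumor-promoting and immunosuppressive activities".
- **Allocation.** The Study Summary plans 28 ketorolac patients per site, and for controls: "About 10 patients will be allocated randomly into the concurrent control group for each disease site separately". Disease site is the only factor by which allocation is separated. The controls are there to supply untreated samples for the correlative studies and secondary endpoints; they are not a comparator for primary safety. Version 7.0 stops NSCLC enrolment at 28 consented patients in total.
- **Biomarker aim.** Section 2.2 asks what impact ketorolac has on inflammatory biomarkers, from samples taken before and after surgery. Section 7.1 adds: "In addition, we will measure NLR, CRP, and IL-6". Section 4.2 labels the correlative studies exploratory.
- **Analysis.** Section 16.2.4 lists descriptive statistics, and says that "graphical displays will be used to characterize central tendency and variability over time", with log transformation as appropriate. It gives no arm contrast, covariate or breakdown by approach. The study calendar in Section 6.1 does not list approach as an item to record.
- **Status.** Section 9 closes enrolment for everyone and ends study assessments and activities for NSCLC participants.

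**The concern.** The objective is causal, and the control group was created to serve it, but the analysis stops short of the comparison. A reader will set the two arms' curves side by side, and nothing in the plan says how large the difference is, how precise it is, or whether the arms had the same kind of operation.

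Approach is the natural factor to look at. If surgical trauma drives the response, as Section 3 says, the extent of the operation may affect the post-operative marker levels. With about 10 controls per site, the open share can differ appreciably between arms by chance. If more controls had open surgery, the ketorolac arm could look less inflamed for that reason; if fewer did, a real effect could be masked. Even with balance, mixed approaches add variance to an already small comparison. At stake is the reading of an exploratory endpoint. The primary safety endpoint does not use the controls and is unaffected.

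**Working it through.** **Inputs from the documents.** 28 ketorolac and about 10 control patients per site. The plan's total reproduces: 2 × 28 + 2 × 10 = 76. For NSCLC, 28 consented in total.

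**Assumptions (not in the documents).** Open-surgery share q of 10% to 50%. Effect of open surgery on a log marker of 0.5 to 1.0 SD (within-approach SD = 1). NSCLC split in the planned ratio: 28 × 28/38 ≈ 21 ketorolac and 28 × 10/38 ≈ 7 control.

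**Step 1: chance of imbalance.** Let a ~ Bin(n₁, q) and b ~ Bin(n₂, q) be the open cases in the ketorolac and control arms. Sum the exact joint probabilities over |a/n₁ − b/n₂| ≥ 0.20 (or 0.30). For the direction that mimics a benefit (more open surgery in controls), sum over b/n₂ − a/n₁ ≥ 0.20 only.

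| Open share q | 28 vs 10: ≥20 points, either direction | 28 vs 10: ≥20 points, mimics benefit | 28 vs 10: ≥30 points, either direction | 21 vs 7: ≥20 points, either direction | 21 vs 7: ≥30 points, either direction |
|---|---|---|---|---|---|
| 10% | 7% | 5% | 1% | 10% (0.095) | 2% |
| 20% | 17% | 9% | 4% | 22% | 7% |
| 30% | 23% | 12% | 7% | 29% | 12% |
| 50% | 31% | 15% | 12% | 33% | 16% |

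**Step 2: what an imbalance does to the observed difference.** Shift = imbalance × approach effect. At 20 points: 0.20 × 0.5 = 0.10 SD to 0.20 × 1.0 = 0.20 SD. At 30 points: 0.15 to 0.30 SD.

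**Step 3: compare with sampling error.** SE of the arm difference = √(1/n₁ + 1/n₂). At 28 vs 10 this is √(1/28 + 1/10) = 0.37 SD; at 21 vs 7 it is √(1/21 + 1/7) = 0.44 SD. Even the 0.30 SD shift is smaller than one standard error.

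**Step 4: what adjustment gains.** Leaving approach out multiplies the SE by √(1 + d²q(1 − q)), where d is the approach effect. At 28 vs 10 with d = 1:
- q = 0.3: √1.21 × 0.368 = 0.405
- q = 0.5: √1.25 × 0.368 = 0.412

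In simulation (20,000 trials per setting, no ketorolac effect, d = 1), adjusting for approach brings the SE to about 0.37. With d = 0.5 the unadjusted values are only √1.0525 × 0.368 = 0.378 and √1.0625 × 0.368 = 0.380, so the gain is slight.

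**Step 5: false-positive rates, had a two-sided 5% test been used.** By simulation at 28 vs 10 with q of 30% and 50%:
- Over all randomisations: about 5%, with or without adjustment.
- In trials with at least 30 points of imbalance, unadjusted: about 7% (d = 0.5) to 12–13% (d = 1).
- In the same trials, adjusted: about 4–5%.

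**The case against.** The strongest reply is that chance imbalance is not bias. Allocation is random and separate by site, and the standard error of an arm difference already covers imbalance in approach. Steps 3 and 5 bear this out: the overall error rate stays near 5%, and the small control group is a larger problem than approach. This stands. What remains is precision and the reading of the single realised trial.

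Second, the endpoint is exploratory and no test is planned, so no formal inference can go wrong. That is fair, and it limits the weight of the point. But an objective about ketorolac's impact cannot be answered without some contrast between arms.

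Third, allowing any standard-of-care approach is a reasonable choice in a safety pilot. Pneumonectomy and recent NSAID use are excluded, further ketorolac during the operation is barred, and a pre-operative sample is taken. All true; nothing here argues for restricting approach.

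Three stronger readings are tempting and are not supported:
- A reader might infer that an imbalance is likely to produce a spurious ketorolac benefit. About half or more of the either-direction probability mimics a benefit (5% to 15%); the rest would hide one. The open share is nowhere stated.
- A reader might infer that the protocol itself says open surgery raises IL-6 or CRP. Section 3 links surgery to inflammation, and surgical trauma to prostaglandins and thromboxanes. It does not compare approaches or name those markers in that context.
- A reader might infer that undefined anaesthesia is a second confounder, for instance through corticosteroids. The documents do not mention corticosteroids or any anaesthetic effect on the markers. Excluding patients by a drug given in theatre could also condition on an event after randomisation.

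**Conclusion.** The point holds as a minor one about an exploratory endpoint. Section 16.2.4 does not deliver the between-arm contrast that the secondary objective and the control group call for, and it leaves out a factor that the protocol's own rationale makes relevant. The consequence is avoidable noise and a possible misreading of one realised trial, not an inflated type I error.

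An imbalance of at least 20 points is neither remote nor expected. Under the stated assumptions, any shift it causes is 0.10 to 0.20 SD, and 0.15 to 0.30 SD at 30 points, against a sampling error of 0.37 SD. The precision gain from adjustment is worth having at a 1 SD approach effect (0.40–0.41 down to 0.37) and slight at 0.5 SD. The lung comparison is the weaker of the two because of the version 7.0 cap. All sizes rest on the assumed open share, the assumed approach effect and, for lung, the assumed 21 to 7 split.

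**What to change.** Enrolment is closed, so allocation cannot change. In Section 16.2.4:

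1. Take approach (open or minimally invasive) from existing operative records for both arms. Use the approach planned before randomisation where it is recorded, because a change during the operation comes after allocation.
2. Tabulate approach by arm within each site.
3. For each biomarker and post-operative visit, report the within-site arm difference in log level, adjusted for approach and the log pre-operative value, with a confidence interval and labelled exploratory. Keep the planned descriptive summaries.
4. Adjust through one common term for approach rather than splitting the arms by approach. At 20% to 30% open, the chance of one or no open case among 10 controls is 38% to 15%. If a site has only one approach, omit the term and say so.
5. For NSCLC, reconcile the record abstraction with Section 9, which ends study activities for those participants.

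This should be written down before the arms are compared. The cost is SAP wording, one abstracted item per patient, and one or two degrees of freedom (approach and the pre-operative value) in a small comparison. Surgery and anaesthesia are not affected.

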### 5.2 Ketorolac

30 mg ketorolac will be administered intravenously during the induction of anesthesia (pre-incision). Ketorolac administration will not be permitted during the operation.

## 6. Procedures Involved

### 6.1 Study Calendar

Tests and Observations	Within 60 days prior to reg.	Before surgery at preoperative visit	Day of surgery (Day 0)				
				3 days	7 days (+/- 2 days)	28 days (+/- 7 days)	1 and 2 years (+/- 3 months)
History, physical, creatinine test, ECOG/Zubrod PS	X						
PET/CT, CT, or MRI scan head, neck, chest, or abdomen per standard of care	X						
Charlson comorbidity index		X					
Blood samples for biomarker analyses*		X	X	X	X	X	
Fresh tissue collection			X				
Adverse event assessment		X		X	X	X	

Chart review or patient contact for survival assessment							X
---	--	--	--	--	--	--	---

\*See section 7.1 Biological Correlative Studies

## 6.2 Procedures

### 6.2.1 Surgical Resection

All patients will receive standard-of-care surgery. Open, video-assisted thoracic surgery, laparoscopy, or robotic surgery are allowed. Standard anesthesia will be administered.

### 6.2.2 Ketorolac

30 mg ketorolac will be administered intravenously during the induction of anesthesia (pre-incision). Ketorolac administration will not be permitted during the operation.

## 6.3 Follow-up

After completion of protocol therapy, patients will be monitored for peri-operative adverse events for up to 90 days after surgery, per routine standard of care for the respective surgical procedure. Patients with benign disease on pathology will still be followed for adverse events for 90 days after surgery, however will not be counted towards the patients analyzed for the study.

Patient charts, institutional renal cell and thoracic surgical databases (Society of Thoracic Surgeons Database), and the Georgia Cancer Registry through the Winship Cancer Institute will be queried to determine patient vital status, status of tumor recurrence if any, and if applicable, cause of death, at 1- and 2-years post-surgery. Only RCC patients will be followed up at 1- and 2-years post-surgery. All study follow-up will cease for NSCLC patients.

## 7. Data and Specimen Banking

### 7.1 Biological Correlative Studies

The specific effects of ketorolac on the host immune system are not known. It is hypothesized that pre-operative ketorolac will enhance anti-tumor immunity and result in activation of tumor-specific T cell responses, as has been noted in our preclinical studies. To verify this, we will collect tissue samples, including surrounding benign and malignant tissue as part of the standard surgical procedure, and peripheral blood at pre-specified time-points. The following samples will be collected from all patients on this trial:

1. Tumor tissue at the time of surgery - Tissue will be collected from patients at the time of surgery by clinical research coordinators from the Clinical Research Unit and taken to [name] lab if adequate tissue is available after all necessary clinical samples are obtained as determined by the pathologist. Tissue analysis will be performed on malignant and benign tissue.
2. Serum and PBMCs before and at time points after surgery - Blood will be collected in CPT from patients at the time of surgery and postoperatively, as delineated in the timeline, by clinical research coordinators.

The following studies are planned in the bio-specimens collected: 1. Flow cytometry (at least to assess proliferating and activated T-cells in blood); 2. TCR sequencing to assess diversity of the T cell repertoire intra tumorally and in blood; and 3. Single cell RNA Seq in blood. Samples will be suitably prepared to allow for this at a future date. Collectively these assays will provide evidence for whether pre-op ketorolac can unleash post-operative anti-tumor T cell response in humans, thus extending the mouse data above. In addition, we will measure NLR, CRP, and IL-6 – all of which have been correlated to prognosis in a number of tumor types at baseline and some of which have been correlated to recurrence outcomes. Additional exploratory studies may also be conducted based on the results of these studies. Peripheral blood mononuclear cells (PBMCs) and plasma will be isolated from CPTs and cryopreserved. The correlative work will be conducted in the lab of [name], [name] and [name].

Tissue analysis: In this proposal, we will measure how organization of immune cells in the tumor change after treatment. The tumor architecture and immune organization will be examined via IF and this imaging data will be quantitatively analyzed. We will determine the relative infiltration of stem-like T-cells, effector-like T-cells, and DCs, lymphatic and blood vessels. We will measure the distance between cells, and quantify their aggregation. We will specifically quantitate regions of sufficient antigen presenting density (5 APCs/100um^2) that are generated following implantation of the niche, and how these regions are located relative to the implant. A specific focus of this work will be how lymphatic and vasculature is altered before and after treatment and how this correlates with response to therapy.

Serum analysis: We will measure NLR, CRP, and IL-6 – all of which have been correlated to prognosis in a number of tumor types at baseline and some of which have been correlated to recurrence outcomes.

PBMC analysis: In ongoing work we have collected blood and tissue from patients receiving checkpoint blockade therapies at Emory and studied the immune response of these patients. We have found that in the blood of patients that have a clinical response to checkpoint therapy, there is a proliferative burst of newly generated effector CD8 T-cells in the blood. In comparison, patients that do not have clinical response to the treatment fail to generate this population of cells. This marker has significant predictive power to identify which patients will respond after the first treatment cycle with PD-1

blockade. In this proposal we will determine if measuring this marker after surgery and treatment with Ketorolac is associated with improved response to treatment.

## 7.2 Blood Sample Collection

Blood samples will be obtained before surgery in the preoperative holding area at the time of routine IV placement and at day 3 after surgical resection. Additional samples will be collected at Day 7 (+/- 2) and Day 28 (+/- 7) post-surgery. Lung resection and nephrectomy patients are typically admitted after surgery. Therefore day 3 blood samples will be obtained while patients are admitted to the hospital. However, if patients are discharged prior to day 3 samples will be collected via mobile blood draw services at patient's home. In addition, study team may use mobile blood draw services to collect some postoperative samples at patients' homes. Tumor samples will be collected from pathology at the time of resection.

CPT tubes should be stored at room temperature following blood collection. CPT tubes should be inverted approximately 10 times after blood collection and kept rocking until processing. CPT tubes should be processed the same day.

Blood specimens taken from	Collected when	Submitted as
PBMCs and plasma: 3 CPTs (8 mL each) of whole blood for collection of plasma and PBMCs	Pre-surgery: at preoperative anesthesia visit and the day of surgery  Post-surgery: Post-operative day 2-3 while in the hospital Between post-operative day 5-20, either prior to discharge or at postoperative clinic visit	Frozen plasma samples containing 2 mL per aliquot in 2 mL cryovials: Cryopreserved PBMCs containing $10^7$ PBMCs per aliquot in 2 mL cryovials

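### Home blood draws occur only after surgery and processing is limited only to the same day, so handling is partly tied to visit while biomarkers are summarised only over time

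*Combined protocol and SAP*

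**What the plan says.** Section 7.2 (Blood Sample Collection) has tubes kept at room temperature and instructs that "CPT tubes should be inverted approximately 10 times after blood collection and kept rocking until processing". The only time limit is that "CPT tubes should be processed the same day"; no number of hours is given.

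Baseline blood is taken on site: "Blood samples will be obtained before surgery in the preoperative holding area at the time of routine IV placement and at day 3 after surgical" (quote cut short). The specimen table in the same section times the pre-surgery tubes "at preoperative anesthesia visit and the day of surgery". Day 3 is in hospital by default, but "if patients are discharged prior to day 3 samples will be collected via mobile blood draw services" at home. The text then adds: "In addition, study team may use mobile blood draw services to collect some postoperative samples at patients' homes". No home draw is mentioned before surgery.

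Section 16.2.4 plans descriptive statistics and graphs of "central tendency and variability over time", with log transformation where suitable. It names no comparison of arms and makes no reference to draw site or delay. Section 1 nevertheless randomises about 10 concurrent controls per disease site, against 28 treated, to supply untreated samples for the correlative studies and secondary endpoints.

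**The concern.** Visit is the only axis along which the markers are to be summarised, and it is also the axis along which draw site changes. If home-drawn tubes wait longer before processing, and if waiting shifts a marker, the shift appears only at post-operative visits and looks like a response to surgery or drug. At Day 3, early discharge decides who is drawn at home, so draw site also follows recovery.

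The readouts at stake are listed in section 7.1: proliferating and activated T cells by flow cytometry, TCR sequencing, single cell RNA Seq, NLR, CRP and IL-6. That section expects the cellular and sequencing assays to show whether ketorolac releases a post-operative anti-tumour T-cell response. A before-and-after difference in handling bears directly on that reading.

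**Working it through.** **Step 1. Where each sample is drawn, as section 7.2 has it.**

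| Visit | Text | Specimen table |
|---|---|---|
| Before surgery | Preoperative holding area | Anesthesia visit and day of surgery |
| Day 3 | Hospital; home if already discharged | Day 2-3, in hospital |
| Day 7 (±2) | Home draw possible | Day 5-20, before discharge or in clinic |
| Day 28 (±7), i.e. Days 21-35 | Home draw possible | No entry |

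The text ties home draws to post-operative visits, though only for some samples. The table lists no home draws at all. Section 7.1 adds that research coordinators collect the blood, which also sits awkwardly with mobile draw services.

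**Step 2. The plan's own figure.** There is none. The documents give no delay times, no share of home draws and no effect of delay on any marker, so nothing can be reproduced. What follows is for scale only.

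**Step 3. Artefact in a change over time.** Let f be the share of samples at a post-operative visit drawn at home, and d the mean shift in those samples from handling, in between-patient SD units. Both are assumed. The artefact in mean change from baseline is f × d.

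- Low: 0.10 × 0.2 = 0.02 SD
- Middle: 0.50 × 0.5 = 0.25 SD
- High: 1.0 × 0.8 = 0.80 SD

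Compare the 95% confidence half-width for a paired mean change with n = 25 per disease site (section 16.2.1) and an assumed correlation ρ between baseline and follow-up: 1.96 × √(2(1−ρ)) / √25.

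- ρ = 0.3: 0.46 SD
- ρ = 0.5: 0.39 SD
- ρ = 0.7: 0.30 SD

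The artefact could be trivial, or it could match or exceed the sampling error. The documents do not say which.

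**Step 4. What happens when arms are compared.** In a treated-minus-control contrast of change at one visit, the artefact becomes d × (f treated − f control). Both arms follow the same visit schedule, and nothing in section 7.2 makes draw site depend on arm, so the expected difference in f is zero. Chance imbalance with 28 v 10 patients has standard error √(f(1−f)(1/28 + 1/10)):

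- f = 0.25: 0.16
- f = 0.50: 0.18

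At d = 0.5, a one-standard-error imbalance leaves 0.5 × 0.16 = 0.08 to 0.5 × 0.18 = 0.09 SD. The contrast itself has standard error √(1/28 + 1/10) = 0.37 SD, taking the SD of change as 1 (ρ = 0.5). The residual is therefore about a quarter of one standard error (0.09 / 0.37 = 0.24). The same-visit comparison removes the systematic part and leaves a small random one.

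The 28 v 10 split is the planned one. Section 1 stops NSCLC at 28 consented patients in total without giving the split, so precision there would be worse.

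**The case against.** The strongest case against is that the causal step is not in the documents. No delay is stated for either setting: a hospital tube can wait and a home tube can be couriered promptly. That is right, and longer delay after home draws is an inference. The link is also partial: Day 3 is in hospital by default, home draws cover only some samples, and if the specimen table governs, the problem largely disappears. Section 1 also mentions an end-of-surgery draw, which is a post-baseline sample taken on site. Section 7.2 already fixes tube, volume, temperature, mixing and a same-day limit, and an hours limit is often left to a laboratory manual. The endpoints are descriptive and exploratory in a pilot. All of this stands, and it keeps the point minor. What it does not remove is that draw site changes with visit under the text of 7.2, and that 16.2.4 names no comparison that would guard against this.

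Two stronger readings are tempting and are not supported.

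- A reader might infer that draw and processing times are not recorded. Section 7.2 is only silent on this; they may be logged on forms outside the documents.
- A reader might infer that ketorolac changes length of stay, through bleeding or pain relief, so that Day 3 home draws differ by arm and bias the contrast. Nothing in the documents shows such an effect, and section 14 expects few adverse events attributable to a single dose. Even an assumed 20-point difference in home draws with a shift of 0.2-0.4 SD gives 0.20 × 0.2 = 0.04 to 0.20 × 0.4 = 0.08 SD, which is 11-22% of the 0.37 SD standard error.

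Timing is a further limit. Section 9 closes enrollment for all patients, although the revision history and section 12 name only the thoracic group. New collection rules may therefore come too late for most or all samples.

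**Conclusion.** The point holds as a minor design weakness confined to secondary and exploratory biomarkers. As section 7.2 is written, draw site is partly tied to visit, time to processing plausibly follows it, and section 16.2.4 summarises only over time, leaving the randomised controls without a stated role in the analysis. A handling shift could therefore be taken for a post-operative change. Its size is unknown and may be negligible: every input to the illustration except the sample sizes is assumed. The conclusion rests on the text, not the table, of 7.2 describing practice, and on home-drawn tubes waiting longer. Neither can be confirmed from the documents.

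**What to change.** **Section 16.2.4.** Compare change from baseline between the randomised ketorolac and control arms at the same visit, within disease site. Tabulate draw location, and draw-to-processing time where it is available, by visit and arm. Repeat the comparison using on-site draws only, as a sensitivity analysis. These steps remain possible after enrollment closes, provided draw location can be retrieved from existing records.

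**Section 7.2.** For any samples still to be taken, require draw time, processing time and draw location. Reconcile the text that allows home draws with the table that lists only hospital or clinic draws, and state the setting of the Day 28 sample.

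**Cost.** Three data fields per sample, some SAP wording and possibly a search of existing laboratory or courier logs. The arm comparison will be imprecise with about 10 controls per site. The on-site-only analysis will be more so, and at Day 3 it drops patients discharged early, so it is a selected subset and should be labelled as such.
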